4.4.6 Post-Hoc Exploratory Analysis

Following the recommendation from the iDMC to halt dosing in Study BN40423, the sponsor decided to perform post hoc exploratory analysis in subgroups defined by baseline age and CAP (thresholds defined based on approximate median splits; i.e., Age < 48 and CAP < 500 ; Age ≥ 48 and CAP < 500 ; Age < 48 and CAP ≥ 500 ; and Age ≥ 48 and CAP ≥ 500). A similar MMRM analysis as the one described in Section 4.4.2 was used, with the addition of the following covariates: subgroup (as categorical), visit-by-subgroup interaction, treatment-by-subgroup interaction and visit-by-treatment-by-subgroup interaction. Age and CAP at baseline were removed from the MMRM analysis. Analyses for this subgroup were performed for the endpoints as listed in Section 4.4.5. For these subgroups defined by baseline age and CAP, strata were defined by post-randomization variables (e.g., patients with low or high exposure) and propensity score methodology was used in order to define the right 'control group'.

by assigning weights (defined as $(PS/[1-PS])$, where PS is the propensity score as estimated using a logistic regression) to placebo patients (to balance out potential confounders) and then employing a weighted regression. The standard errors of the fixed-effects parameters were estimated by using the asymptotically consistent and robust estimator (commonly referred to as the “sandwich” estimator, [Liang and Zeger 1986](#)).

Analyses were performed for the treatment group comparisons of Placebo vs. RO7234292 Q16W.

The following strata were considered:

- Strata split by median of average concentration at Week 21
- Strata split by median of average percent change from baseline in mHTT at Week 21 (due to data availability, the analyses of strata by mHTT might not be completed by the time of the CSR writing so results of this analysis may be reported in an addendum to the CSR)

Those analyses will be re-run on the final data after database lock.

In addition, demographic and baseline characteristics will be summarized by subgroups defined by above mentioned baseline age and CAP using means, standard deviations, medians and ranges for continuous variables and proportions for categorical variables, as appropriate.

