4.4.1 Covariate Adjustment

Unless otherwise noted, analyses of efficacy endpoints (primary, secondary, and exploratory) will include the following covariates in the model:

- Treatment: Placebo, RO7234292 Q8W, and RO7234292 Q16W
- CAG at baseline
- CAG-Age Product (CAP) at baseline (defined as $(CAG-33.66)*age$)
- Age at baseline

For continuous endpoint the baseline of the endpoint will also be included in the model unless stated otherwise.

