4.4.5 Subgroup Analyses

Subgroup analyses will be performed for the following endpoints:

- Change from baseline in cUHDRS and the individual components (TMS, TFC, SDMT, SWRT) at Week 69
- Change from baseline in CSF NfL protein level at Week 69
- Change from baseline in CSF mHTT protein level at Week 69 (due to data availability, the analyses of CSF mHTT protein level might not be completed by the time of the CSR writing so results of this subgroup analysis may be reported in an addendum to the CSR)
- Annualized percent change from baseline in whole and regional brain (caudate and ventricular) boundary shift integrals (BSI) at Week 69

The thresholds for the categories for each variable were chosen on the basis of median or frequency distribution in the population, thus the definitions of the subgroups actually chosen differ slightly from the definitions as specified in the protocol:

- Sex (male versus [vs.] female)
- Age at baseline (≤ 48 years vs. > 48 years (instead of ≤ 45 years vs. > 45 years as planned per protocol))
- CAG repeat length (≤ 44 vs. > 44 [instead of ≤ 43 vs. > 43 as planned per protocol])
- Stage at baseline (Stage I vs. Stage II-IV [instead of Stage I vs. Stage II vs. Stage III as planned per protocol])

For subgroups defined by 'baseline variables' (e.g., baseline_CAG ≤ 44 vs. baseline_CAG > 44), a similar MMRM as the one described in Section 4.4.2 will be used, with the addition of the following covariates: subgroup (as categorical; the corresponding continuous variable will be excluded from the model if it was considered as a covariate in the original model), visit-by-subgroup interaction, treatment-by-subgroup interaction and visit-by-treatment-by-subgroup interaction.

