4.7 BIOMARKER ANALYSES

For statistical modelling, raw concentration values of fluid biomarkers in their respective units will be log-transformed.

Change from Baseline in CSF mHTT Protein Level

The same MMRM model as for efficacy endpoints (see Section 4.4) will be used to model the change from baseline in mHTT (after log-transformation of mHTT). Results from the model will be back-transformed, in order to present model-based percent change in geometric means.

Due to data availability, the analyses of CSF mHTT protein level might not be completed by the time of the CSR writing so results of this analysis may be reported in an addendum to the CSR.

Annualised Percentage Change from Baseline in Whole and Regional Brain (Caudate, and Ventricular) Volume Measured by BSI, as Determined by Structural MRI

The same MMRM model as for efficacy endpoints (see Section 4.4), but without adjusting for baseline volume (as this is already taken into account by considering the percent change from baseline), will be used to model the annualized percent change from baseline in BSI, which means that the measured percent change from baseline to the analysis timepoint will be converted to reflect percent change from baseline normalized for the duration between baseline assessment and post-baseline assessment in years.

Change from Baseline in CSF NfL Protein Level

The same MMRM model as for efficacy endpoints (see Section 4.4) will be used to model the change from baseline in NfL (after log-transformation of NfL). Results from the model will be back-transformed, in order to present model-based percent change in geometric means.

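### The Week 21 mHTT strata select Q16W patients on a post-randomisation outcome without splitting placebo by the same rule; read with Section 4.4.5, the Week 69 mHTT contrast in these strata is circular

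*SAP*

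**What the plan says.** All references are to SAP Version 3. Section 4.4.6 (post hoc exploratory) starts with four subgroups formed from baseline age and CAP, analysed with an extended MMRM. On endpoints it says: "Analyses for this subgroup were performed for the endpoints as listed in Section 4.4.5". Section 4.4.5 lists cUHDRS and its components, CSF NfL, BSI measures and "Change from baseline in CSF mHTT protein level at Week 69".

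Section 4.4.6 then adds strata based on post-randomisation variables. Two are named: a median split of average concentration at Week 21, and "Strata split by median of average percent change from baseline in mHTT at Week 21". The control group is built by giving weights PS/(1-PS) "to placebo patients (to balance out potential confounders) and then employing a weighted regression", with sandwich standard errors. The propensity covariates are not listed. The comparison is fixed: "Analyses were performed for the treatment group comparisons of Placebo vs. RO7234292 Q16W". The section says the analyses will be re-run after database lock and that the mHTT strata may be reported in an addendum to the CSR.

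Section 4.7 analyses mHTT as change from baseline on the log scale. Section 4.4.1 adds: "For continuous endpoint the baseline of the endpoint will also be included in the model unless stated otherwise".

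**The concern.** Drug concentration exists only in treated patients, so some way of constructing a placebo control is needed for the concentration strata. mHTT change is different: placebo patients have it as well, and it moves without drug through natural variation and assay noise. Splitting Q16W at its median puts patients whose mHTT happened to fall by Week 21 into one half and those whose mHTT happened to rise into the other. Placebo, weighted but not split, keeps both kinds.

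If the endpoint is then Week 69 mHTT change, stratifier and endpoint are the same marker measured against the same baseline value. The greater-lowering half will look better than placebo, and the lesser-lowering half worse, even if the drug does nothing. Section 1 says the sponsor was unblinded so that exploratory analyses could inform internal decisions on further development. A spurious gradient across these strata could be taken for exposure-response.

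**Working it through.** The SAP gives no numerical result for these strata, so there is no figure of the plan to reproduce. The 267 patients per arm (Section 2.3) and the roughly 80% who reached Week 69 (Section 2.2) are used only to size the groups: 267 × 0.80 ≈ 214 per arm, and about 54 per age/CAP cell if the four cells are equal (assumption).

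**Model (assumed; the SAP gives no mHTT variances).** Log mHTT at visit t is a stable patient level plus independent visit noise, with total variance 1, between-visit correlation r and no drug effect. Percent change is a monotone function of log change, so a split on a single Week 21 value is the same on either scale. Let D21 and D69 be the changes from baseline y0.

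**Step 1, unadjusted.**
- Var(D21) = Var(D69) = 2(1 − r), and Cov(D21, D69) = 1 − r, so their correlation is 0.5 whatever r is.
- The mean of a normal variable below its median is −√(2/π) = −0.798 SD.
- The greater-lowering half therefore lies 0.798 SD below placebo on Week 21 change and 0.5 × 0.798 = 0.40 SD below on Week 69 change.

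**Step 2, adjusted for baseline as in Section 4.4.1.**
- The part of D69 not explained by y0 is y69 − r·y0, with variance 1 − r².
- Its covariance with D21 is r(1 − r).
- In residual SD units, bias = 0.798 × r(1 − r) / [√(2(1 − r)) × √(1 − r²)] = 0.798 × r / √(2(1 + r)).

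| r | Bias per half (residual SD) |
|---|---|
| 0.5 | 0.798 × 0.289 = 0.23 |
| 0.7 | 0.798 × 0.380 = 0.30 |
| 0.8 | 0.798 × 0.422 = 0.34 |
| 0.9 | 0.798 × 0.462 = 0.37 |

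The other half has the same bias with opposite sign. Fitting the baseline-adjusted regression to simulated data gave 0.24, 0.32, 0.34 and 0.37.

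**Step 3, does the weighting help?** A null-drug simulation (1,000 runs per setting) compared each Q16W half with all placebo patients, using PS/(1-PS) weights fitted on baseline mHTT, baseline adjustment and sandwich errors. Assumed: between-patient log SD 0.40, measurement error SD 0.05 to 0.15, persistent deviation SD 0 to 0.15. At Week 69 the greater-lowering half showed −2.7% to −8.8% and the lesser-lowering half +2.8% to +10.0%. Results with and without weights were practically the same. Baseline covariates do not contain the Week 21 deviation that defines the stratum.

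One setting can be checked against Step 2. With SDs 0.40 and 0.05 and no persistent deviation, r = 0.16/0.1625 = 0.985 and the residual SD is √(0.1625 × (1 − 0.985²)) ≈ 0.070. The bias is 0.798 × 0.985/√3.97 × 0.070 ≈ 0.028, or −2.7%, as simulated.

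**Step 4, false-positive rates at nominal 5%.** In that simulation they were 33–47% per comparison with 54 per arm and 88–96% with 214 per arm. For a smaller bias of 0.24 SD, near the low end of the table, they are about 17% with 54 placebo patients and 53% with 214.

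**Step 5, confirmation of the cause.** When placebo was split at its own median Week 21 change and like halves were compared, the Week 69 null difference was −0.1% to +0.2%, with 5–7% rejection.

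**The case against.** Several objections carry weight.

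- **The endpoint link is inferred.** The endpoint sentence stands before the strata are introduced and speaks of the age/CAP subgroup; the strata have a different method and no endpoint list of their own. This stands: the SAP does not state outright that mHTT change is analysed within the mHTT strata. But the strata sit within those subgroups, no other endpoints are given, and nothing excludes mHTT, so it is the natural reading. That placebo is left unsplit is likewise implied by the weighting, not stated.
- **The propensity covariates are not listed.** True. Only conditioning on placebo patients' own Week 21 mHTT change would address the selection, and the section does not say this is done.
- **The stratifier is an average, which is undefined.** True, but averaging would not rescue it. If k visits with independent noise are averaged, the 2 in Step 2 becomes 1 + 1/k and the bias rises; for k = 2 it is 0.798 × r/√(1.5(1 + r)), or 0.27 to 0.43 for r from 0.5 to 0.9.
- **It is only exploratory.** True, and no primary result depends on it. The label warns of multiplicity and data-driven choice. It does not warn of a contrast that is biased under the null.

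A reader might also infer that effects on NfL or clinical progression would appear in these strata without any drug effect. That needs a correlation between spontaneous mHTT change and those outcomes, and the SAP provides none. A reader might likewise infer that early dropouts remain only in the control. The SAP states no sampling requirement for either arm, so this rests on silence.

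**Conclusion.** The concern holds for Week 69 mHTT within the mHTT-defined strata, on the natural reading of Sections 4.4.5 and 4.4.6. Under no drug effect each half is shifted by about 0.23 to 0.37 residual SD in opposite directions, and weighting on baseline variables leaves this in place. The size rests on the assumed stable-level model and between-visit correlations of 0.5 to 0.9. The direction needs only a positive correlation between Week 21 and Week 69 mHTT given baseline. For cUHDRS and its components, NfL and BSI, bias is possible but neither shown nor quantifiable from the SAP. The argument does not reach the main Week 69 analysis, and the SAP does not present these strata as formal evidence for a responsive subgroup. The point is worth correcting because the biased contrast can be avoided at almost no cost before the planned re-run.

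**What to change.** 1. State in Section 4.4.6 that CSF mHTT is not an endpoint in the strata defined by mHTT change. This removes the circularity.
2. For the remaining endpoints, split placebo at its own median Week 21 mHTT change and report low versus high within placebo as a descriptive negative control. Caution against reading the Q16W strata as exposure-response where placebo shows a similar gradient.

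Do not subtract the placebo gradient from the Q16W contrast. Subtraction is calibrated only if the drug leaves mHTT unchanged. If real, independently varying lowering accounts for a fraction f of the Week 21 change variance in Q16W, the chance component there is √(1 − f) of the placebo one. At an assumed f = 0.5 that is 0.71, so full subtraction would over-correct by 1/0.71 − 1 ≈ 41%.

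The cost is two or three sentences of SAP text and a small additional analysis on data already held, within a re-run that is already planned.

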4.5 PHARMACOKINETIC ANALYSES

For all patients in the PK population, CSF, and plasma concentrations of RO7234292 will be presented descriptively, including arithmetic and geometric means, median, range, standard deviations, and coefficients of variation.

In addition, nonlinear mixed-effects modeling will be used to analyze the concentration–time data for RO7234292 in CSF and plasma following IT administration. A covariate analysis will be conducted to evaluate the effect of covariates such as body weight, age, and sex on RO7234292 exposure. Population and individual estimates of primary PK parameters (e.g., clearance, distribution volume) and secondary PK parameters (e.g., area under the plasma concentration–time curve, average trough plasma concentration) will be computed and used to explore exposure-response relationship on primary and key secondary endpoints, as well as safety measures. The data from this study may be pooled with data from other studies conducted with RO7234292 to support the population PK/PD modeling. Details of this mixed-effects modeling and exploration of exposure-response analysis and results will be described and reported in a document separate from the CSR.

4.6 IMMUNOGENICITY ANALYSES

For the analysis, the following definitions based on Shankar et al. (2014) as well as a Sponsor's definition for ADA with neutralizing potential, will be used to describe patients' RO7234292 immunogenicity as follows:

- **ADA Negative**
 - ADA negative all samples: Patients who have no pre-existing ADA (i.e., antibodies reactive with the drug that are present in patients before treatment) or are missing ADA data before drug administration and who have all negative ADA results following drug administration, and treatment unaffected ADA-negative patients.
 - Treatment unaffected ADA: Subset of ADA negative patients who have pre-existing ADA but do not have a ≥ 4 fold increase in ADA titer following drug administration compared to baseline measurement.
- **ADA Positive**
 - Treatment induced: ADA developed de novo (seroconversion) following drug administration. Patients who have no pre-existing ADA or are missing ADA data before drug administration and who have at least one ADA positive sample following drug administration.
 - Treatment boosted: Patients who have pre-existing ADA and have a ≥ 4 fold increase in ADA titer following drug administration compared to baseline measurement.
- **Transient ADA**
 - Treatment-induced ADA detected only at one sampling time point during the on-treatment or off-treatment follow-up period (excluding the last sampling time point).
- **Persistent ADA**
 - Treatment-induced ADA detected at 2 or more sampling time points during the on-treatment or off-treatment follow-up period; or detected on last sampling time point.
- **ADA with Neutralizing Potential**
 - An ADA positive patient with declining or increasing PK based on visual assessment, and corroborated by PD markers.

Immunogenicity will be analyzed in patients included in the safety population who had at least one ADA assessment. Patients will be grouped according to treatment received or, if no treatment is received prior to study discontinuation, according to treatment assigned. The numbers and proportions of ADA-positive patients and ADA-negative patients at baseline (baseline prevalence) will be summarized by treatment group. For those who are ADA-positive, titers will be estimated as well as antibody subtype. In addition, the numbers and proportions of ADA-positive patients and ADA-negative

patients at baseline (baseline prevalence) and after drug administration (post-baseline incidence) will be summarized for patients on active treatment only.

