3.11 IMMUNOGENICITY ANALYSES

For patients under treatment, there is a potential for them to develop ADA over time. The serum sampling for ADA assessment data will be available for baseline and pre-dose at each time point post-baseline. The immunogenicity analysis population will be used for the analysis. Data will be presented in summary tables (proportions of baseline prevalence and incidence of ADA by treatment arm) and a listing of patients who tested positive for ADA.

The following definitions based on (Shankar, et al., 2014) as well as a Sponsor's definition for ADA with neutralizing potential will be used to describe patients' immunogenicity:

- ADA-Positive
 - Treatment induced: ADA developed de novo (seroconversion) following drug administration. Patients who have no pre-existing ADA or are missing ADA data before drug administration and who have at least one ADA-positive sample following drug administration.
 - Treatment boosted: Patients who have pre-existing ADA and have a ≥ 4 fold increase in ADA titer following drug administration compared to baseline measurement.
- ADA-Negative
 - ADA-negative all samples: Patients who have no pre-existing ADA (i.e. antibodies reactive with the drug that are present in patients before treatment) or are missing ADA data before drug administration and who have all negative

ADA results following drug administration, and treatment unaffected ADA-negative patients.

- Treatment unaffected ADA: Patients who had positive sample at baseline and post-baseline were either negative or positive but do not have a ≥ 4 fold increase in ADA titer following drug administration compared to baseline measurement.

- Transient ADA
 - Treatment-induced ADA detected only at one sampling time point during the treatment or follow-up observation period (excluding the last sampling time point).
- Persistent ADA
 - Treatment-induced ADA detected at 2 or more sampling time points during the treatment or follow-up observation period, or detected on last sampling time point.

Table 1 Overview of Planned Analysis for the Longitudinal Changes Over Time

Parameter	Output presentation		Data Type			Time-points for descriptive statistics	Time points for MMRM	MMRM
	Plot	Table	Absolute	Change	% Change			
mHTT	Y	Y	Y	Y	Y	all available	BSL 1 month to 7 months	Yes
CSF Biomarker (NFL, YKL-40, Tau, and CSF total protein)	Y	Y	Y	Y	Y	all available	BSL 1 month to 7 months	Yes
Plasma NFL	Y	Y	Y	Y	Y	all available	BSL 3 months, 5 months	Yes

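### Post-baseline ADA incidence is tabulated for the active arms only, so background positivity that builds up over repeated sampling is not shown next to the drug arms

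*SAP*

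**What the plan says.** SAP Version 3, section 4.6, defines the set broadly: "Immunogenicity will be analyzed in patients included in the safety population who had at least one ADA assessment". Section 4.1.2 bases the safety population on the ITT population, so placebo patients belong to it.

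Two summaries follow. The first covers ADA-positive and ADA-negative patients "at baseline (baseline prevalence) will be summarized by treatment group". The second covers the same counts at baseline and "after drug administration (post-baseline incidence) will be summarized for patients on active treatment only". No post-baseline summary is planned for placebo.

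The classification rules in the same section are:

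- Treatment induced: "Patients who have no pre-existing ADA or are missing ADA data before drug administration and who have at least one ADA positive sample" after dosing.
- Treatment boosted: "Patients who have pre-existing ADA and have a ≥ 4 fold increase in ADA titer" after dosing.
- Treatment unaffected, counted as negative: "Subset of ADA negative patients who have pre-existing ADA but do not have a ≥ 4 fold increase in ADA titer".
- Transient: treatment-induced ADA found at one sampling time only, other than the last.
- Persistent: treatment-induced ADA found at two or more sampling times, or at the last one.

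Section 2.2.6 defines the endpoint as incidence relative to baseline prevalence. It also lists, as exploratory, the relation of ADA status to efficacy, safety and PK. Section 4.9.2 plans on-treatment adverse event tables by ADA status.

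**The concern.** The treatment-induced label needs one positive among all post-dose samples. An assay with any false-positive rate therefore labels more patients the more often they are sampled, whether or not they received drug. The reference named in the endpoint, baseline prevalence, reflects the pre-dose sample and does not grow in this way. The two quantities are not on the same footing, and the gap between them mixes drug-induced antibody with background.

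Placebo patients are randomised and followed over the same period, so their post-baseline incidence would measure that background directly. The plan leaves it out. A reader of the clinical study report would see the share of active patients classed as treatment induced and could not judge how much of it would have appeared without drug.

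**Working it through.** The SAP states no ADA incidence, assay false-positive rate or ADA sampling schedule for this cohort, so there is no figure to reproduce. What follows is an illustration on assumed inputs.

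**Inputs**

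- f, the false-positive rate per sample: assumed, 0.5% to 2%.
- k, the number of post-dose samples: assumed. Appendix 1 of SAP Version 3 lists nine scheduled weeks after Week 1 up to Week 69 (Weeks 5, 13, 21, 29, 37, 45, 53, 61, 69). It does not say that ADA was sampled at each.
- Errors independent between samples: assumed.
- 267 patients per arm (section 2.3), so 2 × 267 = 534 in the two active arms, used only for scale.

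**Formulae**, for a patient who is truly negative and tested negative at baseline

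- Labelled treatment induced: 1 − (1 − f)^k
- Of these, transient (exactly one positive, not the last): (k − 1) f (1 − f)^(k − 1)
- Persistent: the difference between the two

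**Central illustration, f = 1%, k = 9**

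- Treatment induced: 1 − 0.99^9 = 1 − 0.9135 = 8.6%
- Transient: 8 × 0.01 × 0.99^8 = 0.08 × 0.9227 = 7.4%
- Persistent: 0.0865 − 0.0738 = 0.0127, about 1.3%
- If all 534 active patients met these conditions: 0.0865 × 534 ≈ 46 labelled treatment induced

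**Range of the treatment-induced share**

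| f | k = 3 | k = 6 | k = 9 |
|---|---|---|---|
| 0.5% | 1.5% | 3.0% | 4.4% |
| 1% | 3.0% | 5.9% | 8.6% |
| 2% | 5.9% | 11.4% | 16.6% |

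**Why baseline prevalence does not serve.** With f = 1%, one baseline sample in a truly negative group shows 1% positive. The same group shows 5.9% after six post-dose samples and 8.6% after nine. The difference arises with no drug effect.

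**Why placebo would serve.** With no drug effect and the same sampling, the placebo column has the same expected value as the active columns. With 267 placebo patients and a true background of 8.65%, its standard error is √(0.0865 × 0.9135 / 267) = 1.7 percentage points, which is precise enough to be useful.

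**Pre-existing ADA.** Where a baseline sample exists and detects it, the share misread as induced is 0%, because the patient can only be treatment unaffected or boosted. Where the baseline sample is missing, the share is at most (proportion missing) × (prevalence). With an assumed 1% to 5% missing and 1% to 10% prevalence, this is 0.01 × 0.01 = 0.01% up to 0.05 × 0.10 = 0.5% of active patients, or fewer than three of 534. A falsely negative baseline sample is a further route, which the documents do not allow one to size.

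**The case against.** The case for leaving section 4.6 as it is has substance. The endpoint is defined against baseline, not against placebo. Baseline prevalence is shown for every treatment group. The summary is descriptive, with no test or between-arm contrast. The labels refer to antibody arising after drug, so confining them to drug-exposed patients is a defensible presentation. The transient and persistent classes already set apart most isolated positives: 7.4 of the 8.6 points in the illustration. Positive correlation of assay errors within a patient would lower the figures. All of this stands, and it makes the point minor. It does not supply the background rate over repeated sampling, and a lone false positive at the last sampling time still counts as persistent.

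A reader might infer four stronger things that the documents do not support.

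- *Pre-existing ADA is read as a drug effect.* The fourfold-titre and treatment-unaffected rules prevent this whenever the baseline sample detects it.
- *The plan contradicts SAP Version 1.* Section 3.11 of that version does plan "summary tables (proportions of baseline prevalence and incidence of ADA by treatment arm", but for the Original Design Cohort, which is analysed separately. It shows that the sponsor has used the by-arm layout in this trial, and no more.
- *A placebo column would repair the adverse event tables by ADA status.* It estimates an average background and cannot identify which active patients are false positives. Any dilution in those tables would remain.
- *Background could exceed 20%.* That needs about 2% per sample over 13 samples, which is every scheduled week after Week 1 through Week 101. Dosing stopped on 22 March 2021, when about 80% of participants had reached Week 69 (section 2.2), and section 2 moved patients to the early termination schedule, with telephone calls between clinic visits. Thirteen samples for everyone is not supported.

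**Conclusion.** The point holds as a modest one. Section 4.6 omits the only concurrent randomised estimate of background ADA positivity, and the single-positive rule means that baseline prevalence cannot replace it. The size cannot be established from the SAP. About 8.6% of truly negative patients labelled treatment induced (7.4 points transient, 1.3 persistent) is an illustration that rests on an assumed 1% false-positive rate, nine samples and independence. The misclassification of pre-existing ADA is confined to missing or falsely negative baseline samples; the missing-baseline part is small under the assumptions shown. Sample size, power, type I error and the efficacy analyses are unaffected. This improves a descriptive table and does not correct an error in the plan.

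**What to change.** Change the last sentence of section 4.6 so that post-baseline incidence, with the transient and persistent split, is summarised by treatment group including placebo. For placebo patients, count from the first study injection. Use all available assay results and state the denominator in each arm. Show patients with no baseline ADA sample on a separate line.

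The cost is one more table column and one more line. The downside is that post-baseline placebo samples may not have been assayed. In that case the column is limited to patients with results, and the SAP should say so, so that the reader knows why the comparison is partial or absent.
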